#### Table 1. Table of study treatments and procedures. Abbreviations: PC – Prevention Center.

\*Performed at UWMC. \*\* Performed in [name] lab. Call lab to arrange collection and processing at same time as the bicycle VO2 testing.

# 6.0 SAFETY MONITORING AND ADVERSE EVENT REPORTING

# 6.1 Safety Monitoring

All adverse events will be followed by the PI and study personnel until the events are resolved, the subject is lost to follow-up, or the adverse event is otherwise explained. At the last scheduled visit, the investigator will instruct each subject to report any subsequent event(s) that the subject, or the subject's personal physician, believes might reasonably be related to participation in this study. The investigator will follow any death or adverse event occurring at any time after a subject has discontinued or terminated study participation that may reasonably be related to this study. An internal audit will take place each month of the trial to insure that everything is well documented.

As each of the first five subjects completes the cross-over, we will submit to the IRB a report on how the drug was tolerated. We will report all side effects, adverse events and subject concerns. In the event that one of the first 5 subjects withdraws from the study for reasons related to the drug, we will report immediately to the IRB via modification.

### 6.2 Adverse Event Definitions and Reporting Requirements

### 6.2.1 Adverse Event

Safety information will be assessed initially by subject interview. The clinical research coordinator is responsible for collecting and recording all clinical data. As these results are collected, all adverse events will be identified and reported to the principle Investigators within seven (7) days. Adverse events will be reported as described below (section 6.2.3). The principal investigator (PI) is responsible for evaluating each AE and for determining whether the AE affects the risk/benefit ratio of the study and whether modifications to the protocol and consent form are required. All IRB-approved protocol or consent form revisions that indicate a change in risk for participants will be reported to the National Institute of Diabetes and Digestive and Kidney Diseases (NIDDK) in a timely manner.

Study participants will be provided a telephone number and instructed to contact the study clinician to report any AEs they may experience, except for life-threatening events, for which they will be instructed to seek immediate emergency care. Where feasible and medically appropriate, participants will be encouraged to seek evaluation where the study clinician is based, and to request that the clinician be paged or otherwise contacted upon their arrival. With appropriate permission of the participant, whenever possible records from all non-study medical providers related to AEs will be obtained and required data elements will be recorded on study case report forms. All participants reporting an AE will be followed clinically, until the AE resolves (returns to baseline) or stabilizes.

Study site staff will document on study case report forms all AEs reported by or observed in enrolled study participants regardless of severity and presumed relationship to study product.

All adverse events will be graded as follows:

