# 3.6 Participant Withdrawal

Participants will be allowed to voluntarily withdraw from the study for any reason and at any time. The investigator may withdraw participants from the study in order to protect their safety or if they are unwilling or unable to comply with required study procedures after consultation with the study sponsors and co-sponsors. Participants also may be withdrawn if the study sponsor, government or regulatory authorities, or site IRBs/ECs terminate the study before the planned end date. Reasons for withdrawal from the study will be recorded and a final evaluation will be made if feasible.

Participants who discontinue treatment but remain in the study will continue to be followed-up whenever possible.

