## 4.4 Toxicity Management

Currently, the mechanism whereby Coenzyme Q10 and Nicotinamide Riboside may cause harm or toxicity is unknown. There have been studies demonstrating slightly decreasing hemoglobin and potassium in healthy controls treated with NR^13. In the event of moderate or serious adverse effects (as defined in section 6.2) requiring treatment for such conditions as nausea, vomiting, or abdominal pain thought to be related to toxicity from the study drug, the patient will be withdrawn from the study and adverse events reported.

Mild adverse events that do not requiring treatment and are thought to be potentially related to toxicity from the drug will prompt a 50% dose reduction.

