### Baseline visit

The baseline visit will be the same as visits 2-4 with an additional of medical history and anthropomorphic testing. Subject will undergo a baseline evaluation including a detailed assessment of demographics, smoking history, medical history, medication inventory, vital signs and anthropometrics (height, weight, waist to hip ratio). A pregnancy test will be performed on all women of childbearing potential. If the subjects meet the eligibility criteria the study coordinator will contact the subjects' primary physician regarding the subjects' involvement in the trial.

The study drug dispensed at Baseline visit and Visits 2, 3, 4. The participant will receive either placebo or NR or Coenzyme Q10 from the Investigational Drug Service (IDS) and instructed on how to appropriately administer the medications. He or she will be instructed to take the medication daily starting on the day after the study visit.

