# Washout (week 7 and 14):

After the second visit, the participant will undergo a 1 week washout period prior to initiating the subsequent treatment arm for another 6 week period.

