# 6.2.3 Adverse Event Reporting

Any AE that is unexpected, related to study participation, and serious (defined in 6.2.1) will be reported in writing to the IRB within 7 days of the PI's first knowledge of the event. Any AE that is unexpected, related to study participation, and suggests greater risk of harm than previously known or recognized will be reported in writing to the IRB within 7 days of the PI's first knowledge of the event.

The PI will review all expedited adverse event reports. In addition, any deviations from protocol will be reported to the IRB and copied to the Prevention Center.

A summary of all adverse events and any audit reports will be sent to the IRB. Any action resulting in a temporary or permanent suspension of this study (e.g., IRB actions, or actions by the investigators or co-investigators) will be reported to the appropriate NIDDK program official. In addition, the NIDDK will be given notice of any actions taken by the IRB or regulatory bodies regarding the research and any responses to those actions.

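### Serious adverse events share one 7-day limit for reaching the PI, so a qualifying event may take 14 days to reach the IRB; whether the next product starts before the PI must know turns on a contradiction in section 5.0

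*Combined protocol and SAP*

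**What the plan says.** **Internal reporting.** Section 6.2.1 makes the research coordinator responsible for collecting safety data and states that "all adverse events will be identified and reported to the principle Investigators within seven (7) days". The limit does not vary with seriousness. The same section continues: "The principal investigator (PI) is responsible for evaluating each AE".

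**Serious events.** Section 6.2.2 defines them by reference to US regulations and ICH guidance, including the ICH guideline on expedited reporting. Section 6.2.3 has the PI review expedited reports. Neither says how quickly such a report must reach the PI.

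**IRB reporting.** Under section 6.2.3, events that are unexpected, related, and either serious or suggestive of greater risk than was known go to the IRB "within 7 days of the PI's first knowledge of the event".

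**Other routes.** Section 6.2.1 tells participants to telephone the study clinician about adverse events. Life-threatening events are excepted: for those, participants seek emergency care. Where feasible, they are encouraged to ask that the clinician be paged.

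**Dispensing and start.** Section 5.0, Baseline visit: "The study drug dispensed at Baseline visit and Visits 2, 3, 4". That paragraph goes on to start the medication the day after the visit. Table 1 marks dispensing at baseline, visit 2 and visit 3, and adverse event assessment at visits 2, 3 and 4. Section 5.0, Washout, places a "1 week washout period prior to initiating the subsequent treatment arm".

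**The concern.** A death or hospitalization has the same internal limit as mild nausea, although the plan refers to expedited reporting. The second 7-day clock starts only when the first has ended, so the two limits add up.

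The crossover makes the timing matter more. Each participant moves to a new product twice after the first period, and the visit where adverse events are elicited is also the visit where the next product is handed over. Section 4.4 ties its actions to how severe an event is and whether it is thought to be drug-related. Section 6.2.1 gives evaluation of each event to the PI. If that evaluation can come after the next exposure has begun, the participant may be on a second product before the event under the first has been judged. An event whose cause is assessed late is also harder to attribute to a treatment period. A serious event that bears on risk to other participants may wait a week before the PI must consider it.

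**Working it through.** **Inputs.** Coordinator to PI: 7 days (section 6.2.1). PI to IRB: 7 days (section 6.2.3). Treatment period: 6 weeks; washout: 1 week (section 5.0 and Table 1). Start of next product: the day after the visit (section 5.0, Baseline visit) or after washout (section 5.0, Washout). Day 1 is the first dose. The 7 days are taken as calendar days from collection, and visits as on their nominal day.

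**Step 1: reproduce the plan's calendar.** Visit 2 at week 6; visit 3 at 6 + 1 + 6 = week 13; visit 4 at 13 + 1 + 6 = week 20. This matches the stated visits at weeks 6, 13 and 20 and washouts in weeks 7 and 14. (The 56-day periods in section 2.3 would give weeks 8, 17 and 26, so the visit schedule rests on 6-week periods.)

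In days, visit 2 is 6 × 7 = day 42 and the washout is days 43 to 49. Visit 3 is 13 × 7 = day 91, with washout on days 92 to 98, and the same intervals apply.

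**Step 2: dispensing.** PI deadline = collection day + 7. An event collected at visit 2 is due by 42 + 7 = day 49, but the next product is handed out on day 42, which is 7 days earlier. Events collected on days 36 to 41 are due on days 43 to 48, also after dispensing.

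**Step 3: start of the next product.**

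| Start instruction | First dose | Event collected | PI deadline | Deadline relative to first dose |
|---|---|---|---|---|
| Day after visit | 42 + 1 = day 43 | Visit 2 (day 42) | day 49 | 6 days after |
| After washout | 42 + 7 + 1 = day 50 | Visit 2 (day 42) | day 49 | 1 day before |
| After washout | day 50 | Washout (days 43–49) | days 50–56 | 0 to 6 days after |

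**Step 4: IRB.** For a qualifying event, 7 + 7 = 14 days from collection. For one collected at visit 2 the latest date is 42 + 14 = day 56. That is 56 − 50 = 6 days after the first dose under the washout instruction, or 56 − 43 = 13 days under the day-after-visit instruction.

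**Step 5: search for a faster rule.** Sections 4.4, 6.1, 6.2.2 and 6.2.3 give none for serious events to reach the PI. Section 6.1 requires an immediate IRB report if one of the first five participants withdraws for drug-related reasons, but the trigger there is the withdrawal, not the event.

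**The case against.** **Seven days is a ceiling, and a clinician may know sooner.** This stands. Participants telephone the study clinician, who may also be paged, and reported events are followed clinically. In the screening procedures of section 5.0 the study clinician shares the eligibility decision with the PI, so this person is not a bystander. But the route depends on the participant, the telephone instruction excepts life-threatening events, and nothing limits the time from clinician to PI.

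**The PI is not shown to be the one who acts.** This also stands in part. Section 4.4 says "the patient will be withdrawn from the study and adverse events reported" without naming who decides. Section 3.6 says "The investigator may withdraw participants from the study in order to protect their safety", and section 7.5 likewise refers to the investigator. So it does not follow that the section 4.4 actions must wait for the PI. What follows is narrower: the evaluation that section 6.2.1 assigns to the PI may come late.

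**The equal 7-day figures do not by themselves put the first dose before the deadline.** A reader might infer that, because the reporting limit equals the washout, the next product can start before the PI must know of an event found at the visit. With the washout observed, the documents do not support this: the deadline is day 49 and the first dose day 50. The slack is one day, but the deadline is not missed. A deadline on or after the first dose needs either the day-after-visit instruction or an event collected during washout.

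**Two larger sizes are tempting.** One is that all 30 participants are affected; only those with an event collected around visit 2 or 3 and passed on near the limit are. The other is that any death or hospitalization may take 14 days to reach the IRB; the section 6.2.3 rule covers only events that are also unexpected and related.

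**The start instruction may concern baseline only.** It stands under the Baseline visit heading. But its paragraph opens by naming the later dispensing visits, so the text does not restrict it.

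**Conclusion.** The concern holds as a gap in the reporting rules. The plan allows up to 7 days for a serious event to reach the PI, and up to 14 days from collection for one that is serious, unexpected and related to reach the IRB. Dispensing before the PI must know follows directly from the schedule at visits 2 and 3.

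Starting the next product before the PI must know is conditional. Under the day-after-visit instruction the deadline falls up to 6 days after the first dose. Under the washout instruction a visit event is due one day before it, and only events collected during washout are due on the day of first dose or later, by up to 6 days. The documents do not settle which instruction governs.

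The figures assume calendar days counted from collection and visits on their nominal day. They are upper limits; the documents give no basis for an expected delay or for how many participants would be affected.

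**What to change.** 1. In section 6.2.1, give serious events a separate, shorter limit for reaching the PI, for example one working day from any staff member's awareness, and keep 7 days for other events. Say whether a call or page to the study clinician starts that limit.
2. Reconcile the Baseline visit and Washout paragraphs of section 5.0 on when the product dispensed at visits 2 and 3 is started.
3. Have the sponsor state how the adverse event review at visits 2 and 3 relates to that start.

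Which start instruction applies, and any dose, withdrawal or treatment-start rule, is left to the sponsor.

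The cost is a wording amendment and somewhat faster internal reporting for what should be few serious events. With one working day in place of seven, and no weekend or holiday intervening, the longest path from staff awareness to the IRB for a qualifying event falls from 7 + 7 = 14 days to about 1 + 7 = 8 days.

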#### Severity

- 0 = No adverse event or within normal limits
- 1 = Mild—did not require treatment
- 2 = Moderate—resolved with treatment
- 3 = Severe—required professional medical attention
- 4 = Life-threatening or disabling
- 5 = Death

Related to study procedures (there is a reasonable possibility that the experience may have been caused by the study procedures)

- 0 =Unrelated 1 =Unknown
- 2 = Related

Unexpected event (an AE with specificity or severity not consistent with the risk information in the protocol/application or an AE that has not been previously observed)

0 = No1 = Yes

Serious (any AE occurring at any dose that results in death; a life-threatening adverse drug experience; inpatient hospitalization or prolongation of existing hospitalization; a persistent or significant disability/incapacity; a congenital anomaly/birth defect; or any important medical event that, based on medical judgment, jeopardizes the subject and may require medical or surgical intervention to prevent one of the above outcomes)

0 = No1 = Yes

### 6.2.2 Serious Adverse Event

Serious adverse event (SAE) will be defined per U.S. Code of Federal Regulations (CFR) 312.32 and International Conference on Harmonization (ICH), "Good Clinical Practice: Consolidated Guidance" (E6) and "Clinical Safety Data Management: Definitions and Standards for Expedited Reporting" (E2A), as AE occurring at any dose that:

- Results in death
- Is life-threatening
- Results in persistent or significant disability/incapacity
- Is a congenital anomaly/birth defect
- Requires inpatient hospitalization or prolongation of existing hospitalization

This includes important medical events that may not be immediately life-threatening or result in death, or hospitalization but may jeopardize the patient or may require intervention to prevent one of the outcomes listed above.

Per ICH SAE definition, hospitalization itself is not an adverse event, but is an outcome of the event. The following types of hospitalization do not require expedited reporting:

- Any admission unrelated to an AE (e.g. for labor/delivery, cosmetic surgery, administrative, or social admission for temporary placement for lack of place to sleep)
- Protocol-specified admission (e.g. for procedure required by protocol)
- Admission for diagnosis or therapy of a condition that existed before receipt of study agent(s) and has not increased in severity or frequency as judged by the clinical investigator

# 6.2.3 Adverse Event Reporting

Any AE that is unexpected, related to study participation, and serious (defined in 6.2.1) will be reported in writing to the IRB within 7 days of the PI's first knowledge of the event. Any AE that is unexpected, related to study participation, and suggests greater risk of harm than previously known or recognized will be reported in writing to the IRB within 7 days of the PI's first knowledge of the event.

The PI will review all expedited adverse event reports. In addition, any deviations from protocol will be reported to the IRB and copied to the Prevention Center.

A summary of all adverse events and any audit reports will be sent to the IRB. Any action resulting in a temporary or permanent suspension of this study (e.g., IRB actions, or actions by the investigators or co-investigators) will be reported to the appropriate NIDDK program official. In addition, the NIDDK will be given notice of any actions taken by the IRB or regulatory bodies regarding the research and any responses to those actions.

# 7.0 STATISTICAL CONSIDERATIONS

# 7.1 Review of Study Design

We propose a single-center double blind randomized cross-over trial of NR or CoQ10 supplementation versus placebo. As part of the study there will be a 1-week washout between treatment and placebo arms.

## 7.2 Endpoints

Primary endpoints are change in aerobic capacity using cycle ergometry. Secondary endpoints are change in muscle work efficiency, metabolic response profile and markers of oxidative stress and inflammation.

### 7.2.1 Primary Endpoints

[figure not shown]
Consistent with the primary study objective to test NR and CoQ10 improving aerobic capacity, the following endpoints will be assessed:

• *Physiologic measurements from cycle ergometry:* The main outcome of this study is aerobic capacity (VO2max) using cycle ergometry.

### 7.2.2 Secondary and Exploratory Endpoints

Consistent with the secondary study objective to assess changes in metabolic response profile and markers of oxidative stress and inflammation the following endpoints will assessed:

- Muscle performance using measures of total work and work efficiency which will be obtained by cycle ergometry using standard protocol measuring oxygen uptake starting at 0 watts (W) at 60 rotations per minute (rpm) increasing by 25W every 3 minutes until volitional exhaustion adapting a prior protocol used in CKD patients. 25W of activity is required for grocery shopping and 50W is necessary for household chores. Work efficiency will be calculated as the work performed/energy expended (VO2) above that in cycling 0 watts x 100%. The minimum criteria for a successful efficiency calculation will be a rating of perceived exertion (RPE) of 13 (scale 6-20) or 75% of predicted maximal heartrate. The minimum goal for successfully achieving a VO2max is a RPE of 17 or respiratory exchange ratio≥1.
- PBMC mitochondrial bioenergetic stress test: Monocytes are specifically selected due the strong correlation of their bioenergetics properties with skeletal muscle and cardiac bioenergetics in the primate model. Blood samples will be process using an established protocol. Monocyte will be isolated using magnetic-activated cell sorting (MACS) and CD14+ microbead selection. Bioenergetics analysis will be performed using the Seahorse Biosciences XF24

**Figure 2.** Illustration of monocyte bioenergetic stress test to determine reserve capacity. Abbreviation: oligo=oligomycin, AntiA=antimycin A, FCCP=uncoupler.

extracellular flux analyzer per protocol. Max-OCR (maximal respiration) is calculated after the addition of FCCP, a mitochondrial uncoupler. RC is calculated as the difference of Max-OCR and Basal-OCR (Figure 2).

- Improvement in metabolic response profile suggested by:
  - Change in targeted metabolomics profile using liquid chromatography high-resolution mass spectroscopy (LC-MS) using plasma and urine samples
  - *Oxidative stress biomarkers:* Plasma F2-isoprostanes will be measured by GC-MS as described by Roberts and Morrow.
- Patient reported outcomes: Patient reported fatigue will be assessed using the PROMIS Fatigue Short form 17 and PROMIS Physical function short form 20a. Heart failure symptoms will be assessed using Kanasas City Heart Failure Questionnaire.

# **Exploratory Endpoints**

- Magnetic Resonance Spectroscopy: Leg MRS will serve as a secondary outcome. As mentioned above, only 4 MRS will be obtained as part of this study (at Baseline, visit 2, 4 and 6). MRS will be used to measure phosphorylation capacity (ATPmax) tibialis anterior leg skeletal muscle. These functional tests assist to perturb the cell physiological state in order to measure the contents and dynamics of key metabolic compounds important in mitochondrial energy flux. P MRS is reliable with a documented coefficient of variation for oxidative phosphorylation of 5.1% and has a strong correlation with VO2max.
- *Muscle Fatigue:* We will test muscle fatigability at each follow-up visit. We will test the TA muscle and determine the isometric force generated at 70% of maximal voluntary contraction (MVC) against a force transducer. Using labview software to measure and record the force-time waveform of each contraction we will initiate the protocol at 50 contractions per minute at 70% MVC for one minute. At each 1 minute increment will increase the contraction rate by 10 contractions per minute and reassess the subjects relative perceived exertion on a scale of 1-10 until the patient can no longer maintain the contraction waveform.

